## Non-interventional Study Protocol

Document Number:	c14460058-01
BI Study Number:	1160-0280
BI Investigational Product(s):	Dabigatran etexilate (Pradaxa®)
Title:	Non-Interventional, cross-sectional study to describe health-related quality of life among controlled and uncontrolled patients with nonvalvular atrial fibrillation on anticoagulants. RE-QUOL study.
Brief lay title	Health related quality of life in patients on anticoagulants
Protocol version identifier:	1.0
Date of last version of protocol:	05 January 2017
PASS:	No
EU PAS register number:	EU PAS 16988
Active substance:	B01AE07 - Dabigatran etexilate
Medicinal product:	Dabigatran etexilate
Product reference:	EU/1/08/442
Procedure number:	EMEA/H/C/829
Marketing authorisation holder(s):	Boehringer Ingelheim International GmbH [name]
Joint PASS:	No
Research question and objectives:	
There is a dearth of evidence regarding Health Related Quality of Life (HRQoL) in controlled and uncontrolled patients on oral anticoagulants.
 
The present study has been designed to describe the HRQoL in patients with non valvular atrial fibrillation (NVAf) receiving conventional vitamin K antagonist (VKA) but no controlled and those controlled who received VKA or direct oral anticoagulant

	(DOAC). Primary objective: The primary objective of the study is to describe the HRQoL in uncontrolled patients treated with VKA and controlled patients treated with VKA or DOAC. Secondary objective: The secondary objective is to describe the profile of uncontrolled patients
Country(-ies) of study:	Spain
Author:	(Outsourced Trial Clinical Monitor)  Mobile:
Marketing authorisation holder(s):	Boehringer Ingelheim International GmbH [name]
Date:	05 January 2017
Page 2 of 39	
Proprietary confidential information © 2017 Boehringer Ingelheim International GmbH or one or more of its affiliated companies. All rights reserved. This document may not - in full or in part - be passed on, reproduced, published or otherwise used without prior written permission	

## 2. LIST OF ABBREVIATIONS

ADR	Adverse Drug Reaction
AE	Adverse Event
AESI	Adverse Event of Special interest
AF	Atrial Fibrillation
CA	Competent Authority
! "# \$ % & ' ( # & ) * ) + , -	! + / - * 0 1 2 - 3 - 4 , 0 5 4 1 6 7 , - 8 9 : - , 0 - * 1 + . 8 # / - ; < = > ? 8 % 1 4 @ - 0 - 1 - 6 6 1 0 7 * 8 0 , + B - C D E ( # * ) 7 6 4 , F 1 * - 4 * - 8 / - G > = H & & - I ! 4 0 - / + , 9
CI	Confidence Interval
CML	Local Clinical Monitor
CRA	Clinical Research Associate
CTCAE	Common Terminology Criteria for Adverse Events
DMP	% 4 0 4 4 . 4 / - A - . 0 K 6 4 .
DOAC	% 1 , - ) 0 L , 4 6 # . 0 1 ) + 4 / 7 6 4 . 0
eCRF	Electronic Case Report Form
ENCePP	European Network of Centres for Pharmacoepidemiology and Pharmacovigilance
FDA	Food and Drug Administration
GCP	Good Clinical Practice
GEP	Good Epidemiological Practice
GPP	Good Pharmacoepidemiology Practice
GVP	Good Pharmacovigilance Practices
MK ( ! D !	M 6 + @ 4 6 K 3 4 , A 4 ) + 2 1 / 1 6 4 . ) - ! 6 1 . 1 ) 4 6 D , 1 4 6 ! + + , F 1 . 4 0 + ,
" # & ' N O P %	" 9 : - , 0 - * 1 + . 8 # @ . + , A 4 6 , - 4 6 4 . F 6 1 2 - , 5 7 . ) 0 1 + . 8 & 0 , + B ; Q : + 1 . 0 ? 8 N 6 - - F 1 / 3 1 * 0 + , 9 + , ; - F 1 * : + * 1 0 1 + . 8 0 4 @ 1 6 - E R S 8 P 6 F C 6 9 9 - 4 , * ? 8 % , 7 / * 4 . F # 6 ) + 3 + 6 T
" S U + O	" - 4 6 0 3 , - 6 4 0 - F U 7 4 6 1 0 9 5 0 1 5 -
E ! & S	E . F 1 2 1 F 7 4 6 1 * - & 4 5 - 0 8 - : + , 0
EP !	E . F - : - F - . 0 P 0 3 1 ) * ! + A A 1 0 0 - -
ERS	E . 0 - , 4 0 1 + . 4 6 R + , A 4 6 1 V - S 4 0 1 +
E & W	E . 2 - * 0 1 / 4 0 + & 1 0 W 1 6 -
OK ( J	O + ) 4 6 K 3 4 , A 4 ) + 2 1 / 1 6 4 . ) - J 4 . 4 / - ,
O ( P W	Left Ventricular Ejection Fraction
J # "	J 4 , B - 0 1 . / # 7 0 3 + , 1 V 4 0 1 # ! + 6 F - ,
R ( # W	R + . ' ( 4 6 2 7 6 4 , # 0 , 1 4 6 W 1 @ , 1 6 6 4 0 1 + .
L # !	L , 4 6 4 . 0 1 ) + 4 / 7 6 4 0 1 + .
& # P	& - , 1 + 7 * # F 2 - , * - P 2 - . 0
& %	& 0 4 . F 4 , F % - 2 1 4 0 1 + .
& # K	& 0 4 0 1 * 0 1 # 4 6 9 * 1 * K 6 4 .
& A K !	& 7 A A 4 , 9 + 5 K , + F 7 ) 0 ! 3 4 , 4 ) 0 - , 1 * 0 1 ) *
& L K	& 0 4 . F 4 , F L : - , 4 0 1 . / K , + ) - F 7 , -
DDS	D 1 A - 1 . D 3 - , 4 : - 7 0 1 ) S 4 . / -
( X #	( 1 0 4 A 1 . X # . 0 4 / + . 1 * 0

#### 4. ABSTRACT

Name of company: Boehringer Ingelheim			
Name of finished medicinal product: Pradaxa®			
Name of active ingredient: B01AE07 - Dabigatran etexilate			
Protocol date: 05 Jan 2017	Study number: 1160-0280	Version/Revision:	Version/Revision date:
Title of study:	Non-Interventional, cross-sectional study to describe health-related quality of life among controlled and uncontrolled patients with nonvalvular atrial fibrillation on anticoagulants. RE-QUOL study		
Rationale and background:	
The present study has been designed to describe the HRQoL in patients with non valvular AF receiving conventional VKA but no controlled and those controlled who received VKA or DOAC.
 
The type of patients to be included in this study are those seen in Internal Medicine, i.e. elderly patients, chronically ill, mostly hospitalized, polymedicated, and at high thromboembolic and bleeding risk. The present study will provide valuable data about the HRQoL of these patients regarding their anticoagulation status (controlled or non-controlled).
		
Research question and objectives:	
There is a dearth of evidence regarding HRQoL in controlled and uncontrolled patients on oral anticoagulants.
 
The present study has been designed to describe the HRQoL in patients with non valvular AF receiving conventional VKA but no controlled and those controlled who received VKA or DOAC.
 
Primary objective: to describe the HRQoL in uncontrolled patients treated with VKA and controlled patients treated with VKA or DOAC.
 
Secondary objective: to describe the profile of uncontrolled patients
		
Study design:	
This observational multicenter and cross-sectional study will be conducted in Departments of Internal Medicine from approximately 50 centers in Spain
 
Approximately 500 patients seen in internal medicine are planned to be included in the study. To minimize selection bias at the patient level, consecutive patients from each site who meet entry criteria will be enrolled. The 3 participating autonomous communities planned are Madrid, Valencia and Andalucía. Patients should be included in a ratio 2:1, 2 patients controlled (VKA patients with a Time in Therapeutic range TTR ≥ 65% and all DOAC patients) per 1 patient uncontrolled (VKA patients with a TTR < 65%), due to the controlled patients comprise more treatments.
 
Control will be considered when INR values are between 2 and 3.
 
The design of the study impose an only visit to be performed that will
		

	
coincide with one of those performed by the patients as part of routine follow-up of their disease, without interfering with usual clinical practice of the investigator. A specific therapeutic strategy has already been assigned based on routine practice, and without interference with the physician's prescription habits. The observational nature of the study is ensured as no diagnostic or therapeutic intervention outside of routine clinical practice will be applied.

Population:	
Patients with non-valvular atrial fibrillation who are on the same anticoagulant therapy (VKA or DOAC) during at least 6 months and maximum 2 years will be included.
 
The patient will be considered included when he/she agrees to participate in the study by signing the informed consent.
 
The patient will be classified between controlled or uncontrolled group depending on the %TTR if VKA patients. If the %TTR collected from the analytical records was obtained by the Rosendaal method, VKA patients with a TTR < 65% will be allocated to the uncontrolled group and VKA patients with a TTR ≥ 65% will be allocated to the controlled group). If the %TTR was obtained by the direct method, the patient will be considered uncontrolled or controlled depending on whether the TTR value is < 60%. All DOAC patients will be allocated to the controlled group.

Variables:	
Quality of life: HRQoL will be based on the patients' ratings on Sawicki questionnaire completed during the only study visit. This questionnaire includes 32 items grouped in 5 dimensions – treatment satisfaction, self-efficacy, strained social network, daily hassles and distress. Higher scores indicate lower HRQoL.
 
Uncontrolled patient profile: demographic characteristics (age, gender, work status, life status, etc), CHA2DS2-VASc, HAS-BLED, AF diagnosis date, VKA treatment, time since treatment initiation, time since patient is uncontrolled (if assessable) left ventricular ejection fraction, Kidney function (creatinine clearance), concomitant diseases, concomitant treatments, frequency of visits to the physician, and history of thromboembolic and bleeding events

Data sources:	
Data collection will be limited to those available in the medical records of selected patients and the questionnaire necessary to evaluate the primary objective of the study, of patients in whom a specific therapeutic strategy has already been assigned based on routine practice, and without interference with the physician's prescription habits

Study size:	
It is planned that a total of approximately 330 patients will be recruited for the controlled group and 170 patients will be recruited for the uncontrolled group.
 
Based on such sample size estimates, categorical variables of binomial proportions (e.g. gender) will be estimated with the precision (i.e. width of descriptive 95% confidence interval) described in Table 9.5: 1, according to the prevalence of the attribute.

Data analysis:	
To describe the quality of life among patients controlled and uncontrolled: The primary outcome of the study is the health-related

	
quality of life as measured by the Sawicki questionnaire. The scores of each individual question will be summarized descriptively in the controlled and uncontrolled patients. In addition, the summary score for each dimension of the questionnaire will be calculated for each patient by dividing the total score by the number of items included in that dimension and summarized in the same way as the individual questions.
 
To describe the profile of uncontrolled patients treated with vitamin K antagonists: The specified variables in Section 9.3.2.2 [demographic characteristics (age, gender, work status, life status, etc), CHA2DS2-VASc, HAS-BLED, AF diagnosis date, VKA treatment, time since treatment initiation, time since patient is uncontrolled (if assessable) left ventricular ejection fraction, Kidney function (creatinine clearance), concomitant diseases, concomitant treatments, frequency of visits to the physician, and history of thromboembolic and bleeding events] will be summarized descriptively.
 
Missing data will not be imputed and will be left as lost.

Milestones:	
Note that the times described below may be modified by the administrative processing periods for study initiation
 

- Final Protocol: January 2017

- start of data collection: March 2017

- end of data collection: September 2017

- final study report: December 2017

## **5. AMENDMENTS AND UPDATES**

None.

## **6. MILESTONES**

Milestone	Planned Date
IEC approval	January 2017
Start of data collection	March 2017
End of data collection	September 2017
Registration in the EU PAS register	December 2016
Final report of study results:	December 2017

## **7. RATIONALE AND BACKGROUND**

Atrial fibrillation (AF) affects 1-2% of general population, but specially persons between 80 - 85 years, in whom the prevalence can reach 16% [1-3]. The first oral anticoagulants to prevent the risk of thromboembolic events in AF were the vitamin K antagonists (VKA) warfarin and acenocoumarol. The management of these agents remains problematic because they need routine coagulation monitoring, clinical surveillance and continuous patient education, affecting to their daily habits and in consequence to their quality of life [4]. Also, data show that 80% of patients continue receiving acenocoumarol in Spain, with a percentage of International Normalized Ratio (INRs) in therapeutic range between 44%-59% [5,6], and mean time in therapeutic range (TTR) of 64% [5].

The direct oral anticoagulants (DOAC) maintain the benefits of anticoagulant therapy and may increase perception of quality of life among patients because they not necessitate the strict monitoring required for VKA. On the other hand maintaining a stable level of anticoagulation with DOACs prevents uncontrolled patients as well as the increased number of monitoring visits for this reason. Theoretically, this fact would have positive implications in quality of life. However, the available evidence from the study of quality of life, does not suggest that patients have large decrements in their quality of life because of suffering from FA. In this sense, the study of Roalfe et al., cross sectional in 1762 patients over 75 years and suffering AF, concluded that in absence of comorbidity, chronic AF has little impact on generic QoL [7]. This suggests that treatment strategies should focus on the prevention of complications such as stroke, so it is necessary to go depth in the study of the anticoagulant therapy and the impact in QoL.

HRQoL was assessed in a sub-group of the overall RE-LY population to measure the effect of the choice of anticoagulant during a stable phase of treatment in the first year of the study, in patients without outcome events, such as strokes or major bleedings [8]. HRQoL was assessed using the EQ-5D, a generic measure of health outcome. Over the course of one year, all anticoagulated patients without outcome events had stable HRQoL. Scores between dabigatran and warfarin were comparable. There is a dearth of evidence regarding HRQoL in controlled and uncontrolled patients on oral anticoagulants.

The present study has been designed to describe the HRQoL in patients with non valvular AF receiving conventional VKA but no controlled and those controlled who received VKA or DOAC.

Since the type of patients to be included in this study is that seen in Internal Medicine, i.e. elderly patients, chronically ill, mostly hospitalized, polymedicated, and at high thromboembolic and bleeding risk, the present study will provide valuable data about the HRQoL of these patients regarding their anticoagulation status (controlled or non-controlled).

## **8. RESEARCH QUESTION AND OBJECTIVES**

The present study has been designed to describe the HRQoL in patients with non valvular AF receiving conventional VKA but no controlled and those controlled who received VKA or DOAC.

The primary objective of the study is to describe the HRQoL in uncontrolled patients treated with VKA and controlled patients treated with VKA or DOAC.

The secondary objective is to describe the profile of uncontrolled patients

[figure not shown]
## 9. RESEARCH METHODS

### 9.1 STUDY DESIGN

This observational multicenter and cross-sectional study will be conducted in Departments of Internal Medicine from approximately 50 centers in Spain.

The design of the study impose an only visit to be performed that will coincide with one of those performed by the patients as part of routine follow-up of their disease, without interfering with usual clinical practice of the investigator. A specific therapeutic strategy has already been assigned based on routine practice, and without interference with the physician's prescription habits. The observational nature of the study is ensured as no diagnostic or therapeutic intervention outside of routine clinical practice will be applied. Figure 1 shows the design of the study.

**Figure 1. Design of the study**

[figure not shown]

### 9.2 SETTING

Approximately 500 patients seen in internal medicine are planned to be included in the study. To minimize selection bias at the patient level, consecutive patients from each site who meet entry criteria will be enrolled. Patients should be included in a ratio 2:1, 2 patients controlled (VKA patients with a TTR  $\geq$  65% and all DOAC patients) per 1 patient uncontrolled (VKA patients with a TTR < 65%), due to the controlled patients comprise more treatments.

The patient will be classified between controlled or uncontrolled group depending on the %TTR if VKA patients. If the %TTR collected from the analytical records was obtained by the Rosendaal method, VKA patients with a TTR < 65% will be allocated to the uncontrolled group and VKA patients with a TTR  $\geq$  65% will be allocated to the controlled group. If the %TTR was obtained by the direct method, the patient will be considered uncontrolled or controlled depending on whether the TTR value is < 60%. All DOAC patients will be allocated to the controlled group. [See figure 2 below.](#)

Figure 2. Patient allocation

If %TTR is not available on analytical records, investigator will calculate it using the last 6 months INR values (at least 4 INR values during the last 6 months). To perform the calculation, it is recommended to avoid periods of anticoagulation initiation and periods with treatment interruptions due to surgery or bleedings.

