#### **9.3.2.2 Secondary outcomes**

The secondary outcome is the uncontrolled patient profile and will be defined by the following variables collected from patient medical records: demographic characteristics (age, gender, work status, life status, etc), CHA2DS2-VASc, HAS-BLED, AF diagnosis date, VKA treatment, time since treatment initiation, time since patient is uncontrolled (if assessable) left ventricular ejection fraction, Kidney function (creatinine clearance), concomitant diseases, concomitant treatments, frequency of visits to the physician, and history of thromboembolic and bleeding events.

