#### 9.10.2.2 Direct access to source data and documents

The investigator / institution will permit study-related monitoring, audits, IEC review and regulatory inspection, providing direct access to all related source data / documents. eCRFs and all source documents, including progress notes and copies of laboratory and medical test results must be available at all times for review by the sponsor's clinical study monitor, auditor and inspection by health authorities. The Clinical Research Associate (CRA) / Clinical Monitor Local (CML) and auditor may review all eCRFs, and written informed consents. The accuracy of the data may be verified by reviewing source documents.

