### **SCREENING CRITERIA:**

- *The patient is willing to participate and grants his or her informed consent to participate in the study in writing.* The date of informed consent must be provided; it must be before or on the same date as the baseline visit.
- *The patient is at least 18 years old.* The patients' age must be 18 years or more (calculated from date of birth to the date of the baseline visit).
- *The patient has a diagnosis of NVAf.* The information regarding the NVAf-type variable must be completed.
- *The patient has been receiving the same anticoagulant treatment (VKA or DOAC) for at least 6 months and up to 2 years.* Time of treatment from the treatment start date to the date of the baseline visit must be at least 6 months and no greater than 2 years.
- *If he/she receives treatment with VKA, availability of TRT% in previous analytical records or sufficient INR determinations to calculate same.* If the patient is receiving treatment with VKA, the TRT% figure must be completed.

If there is a contradiction between the binary variables and the information shown in the CRF in question, the latter shall be assumed to be valid.

The number of unassessable patients in the study shall be provided, together with the reasons for their non-inclusion.

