**The analyses will be performed with the eligible patients.**

# REQUOL Study

## 5 DESCRIPTIVE ANALYSIS.

### 5.1 Groups

The number of controlled vs uncontrolled patients shall be described.

The allocation of each patient to each group is performed automatically by the platform where the data are collected during the study and is performed at the time the VKA and TTR data are collected.

Patients receiving AVK and TTR (Rosendaal method) <65%, or TTR (direct method) <60% are assigned to the uncontrolled group. The rest of the patients are assigned to the controlled group.

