## **REQUOL Study**

- Age at date of diagnosis
- Time since treatment initiation, calculated as the time from the treatment start date to the date of the baseline visit
- Time during which the patient has not been controlled, calculated as 100-TTR% (Rosendaal method)

The categorical variables to be described are: N and (%):

- TTR% (Rosendaal method): TTR < 65%, TTR >=65%
- TTR% (direct method): TTR < 60%, TTR >=60%
- Type of NVAf
- Current type of anticoagulant medication
- Specify VKA

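### Does the plan need to name one TTR method for values that investigators calculate themselves, given that the control cut-off differs by method?

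*Protocol*

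**What the plan says.** Protocol 9.2 classifies VKA patients by TTR and ties the cut-off to the method behind the value: 65% for Rosendaal, 60% for direct. All DOAC patients count as controlled. SAP 5.1 repeats the rule and has the data platform apply it automatically: "Patients receiving AVK and TTR (Rosendaal method) <65%, or TTR (direct method) <60% are assigned to the uncontrolled group". Everyone else is controlled.

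For a VKA patient with no TTR on record, Protocol 9.2 says the "investigator will calculate it using the last 6 months INR values (at least 4 INR values during the last 6 months". The only further guidance is that "it is recommended to avoid periods of anticoagulation initiation and periods with treatment interruptions due to surgery or bleedings". The abstract gives the target range: "Control will be considered when INR values are between 2 and 3". The SAP's eligibility check asks only for a value: "If the patient is receiving treatment with VKA, the TRT% figure must be completed".

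SAP 5.3 tabulates TTR separately for each method. It names Rosendaal alone for one derived item: "Time during which the patient has not been controlled, calculated as 100-TTR% (Rosendaal method". That defines a descriptive variable and does not tell the investigator how to calculate a missing TTR.

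**The concern.** The controlled/uncontrolled split defines the groups in the quality-of-life tables of SAP 8.1 and the whole population for the secondary objective. If the cut-off depends on the method and nobody is told which method to use, investigators at about 50 sites could sort identical INR histories differently.

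The route is also a regular one: inclusion criterion 5 admits VKA patients who have enough INRs for a calculation but no recorded TTR. The variables table in Protocol 9.3 lists TTR but not dated INRs, so an analyst could not recompute every value under one rule without querying sites. With few INRs the direct method is coarse, which makes its 60% cut-off behave unevenly.

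**Working it through.** The documents state no figure on this point, so there is none to reproduce. They also define neither method. The check assumes the usual definitions: Rosendaal interpolates the INR linearly between tests and takes the share of time within 2 to 3; direct is the share of INR readings within 2 to 3.

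**Can the same INRs change group?** Take four equally spaced INRs, the minimum number allowed.

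| INRs | Rosendaal (cut-off 65%) | Direct (cut-off 60%) |
|---|---|---|
| 1.9, 2.5, 2.5, 3.1 | (0.5/0.6 + 1 + 0.5/0.6)/3 = 88.9%, controlled | 2/4 = 50%, uncontrolled |
| 2.2, 1.5, 2.2, 2.5 | (0.2/0.7 + 0.2/0.7 + 1)/3 = 52.4%, uncontrolled | 3/4 = 75%, controlled |

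So they can, in both directions.

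**How coarse is the direct method?** The smallest attainable value that meets 60% is 3/4 = 75% with 4 INRs, 3/5 = 60% with 5, 4/6 = 67% with 6 and 5/7 = 71% with 7.

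**How often do the rules disagree?** All inputs here are assumptions: lognormal, autocorrelated INRs over 180 days; 4 to 9 readings; median 2.2 to 2.6; within-patient log-SD 0.15 to 0.35; between-patient log-SD 0 to 0.20; correlation time 1 to 90 days. In settings with mean Rosendaal TTR of 59 to 69% (Protocol 7 cites 64%), disagreement was 4.5 to 24.8% with equal spacing and 7.0 to 26.3% with irregular spacing. A simpler simulation (median 2.45, log-SD 0.20 to 0.35, 4, 6 or 7 readings) gave about 10 to 21%. In a coarser run (6 to 20%), the highest values came from settings with no true difference in control between patients; at a between-patient log-SD of 0.20, the settings examined gave about 6 to 10%.

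**What does that mean in patients?** Disagreement is a ceiling on inconsistency. If investigators split evenly between methods, the share classified otherwise than under any single named method is half of it: 0.5 × 4.5% = 2.25% to 0.5 × 26.3% = 13.15%. For scale, assume half of the 330 controlled patients take a VKA, giving 170 + 165 = 335 VKA patients.

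- If 10% lack a recorded TTR (33.5 patients): 33.5 × 0.0225 = 0.8 to 33.5 × 0.1315 = 4.4 patients.
- If 50% lack one (167.5 patients): 167.5 × 0.0225 = 3.8 to 167.5 × 0.1315 = 22.0 patients.

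The documents give neither the 335 nor the 10% or 50%.

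**Is one rule better?** When both were compared with the full simulated INR path, again on assumed inputs, neither was consistently closer to the true TTR.

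**Excluded periods.** Take INRs 2.5, 2.5, 2.5, 3.4, 3.4 on days 0, 30, 120, 150, 180, with days 30 to 120 excluded. The interval from day 120 to 150 contributes 30 × 0.5/0.9 = 16.7 days in range. Interpolating across the gap gives (30 + 90 + 16.7)/180 = 75.9%; dropping it gives (30 + 16.7)/90 = 51.9%. The group changes, but only because half of the 180-day window is excluded. Leaving such periods out is the natural reading of the recommendation, and inclusion criterion 4 (at least 6 months on the same therapy) puts initiation largely outside the window.

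**The case for a change.** The strongest case for a change is that the groups being described should be reproducible. A descriptive aim does not remove that need. The by-method rows in SAP 5.3 would show which method was used but could not undo a mixture. The eCRF already calculates creatinine clearance and two risk scores, so calculating TTR from dated INRs would be feasible.

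Much of this is true. The visible text has a gap, and the worked series do change group. What does not follow is that the allocation is defective. The dependence on method comes from the deliberate acceptance of two methods with two cut-offs, and it applies equally to TTRs taken from records. A rule for calculated values would leave that mixture in place and act only on a subset of unknown size.

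The method must in any case be captured, because SAP 5.1 allocates by it and SAP 5.3 tabulates by it. The INRs remain verifiable at site: source documents "including progress notes and copies of laboratory and medical test results must be available at all times for review". Figure 2, on patient allocation, comes just before the sentence at issue and is not shown; it or the platform specification may name the method.

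The derived item in SAP 5.3 adds little. It differs from the protocol's "time since patient is uncontrolled (if assessable", but that mismatch has no bearing on how a missing TTR is calculated.

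**Conclusion.** This is missing detail that investigators and analysts can fill within the plan's own rules, and no change is called for. A TTR calculated by either method has a stated cut-off and so a defined group. The disagreement of roughly 5 to 25% rests entirely on assumed INR distributions. It measures how far two accepted rules differ, not how many patients are placed wrongly, and it concerns only VKA patients without a recorded TTR. DOAC patients are untouched.

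Naming a method would be tidier, but no gain in accuracy can be shown for either choice. Nor can any effect on the quality-of-life summaries, in a study that tests no hypothesis and disclaims causal inference (Protocol 9.9). The conclusion assumes that the method is recorded with each TTR, as SAP 5.1 and 5.3 require in order to work. It would need another look if most VKA patients turned out to have no recorded TTR.
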